9.3.6.4. Potential Immune-mediated Diseases (for HZ/su and mRNA-1273 booster cohort only)

Number and percentage of participants reporting pIMDs from first vaccination up to 30 days post-last vaccination and from first vaccination up to study end will be summarized for all study groups (HZ/suSeq, HZ/suCoAd, overall). All pIMDs will be summarized by MedDRA SOC and PT. pIMDs will also be listed. Any related pIMD will also be presented for study groups (HZ/suSeq, HZ/suCoAd and overall).

9.3.6.5. Adverse events of special interest

Number and percentage of participants reporting AESIs from first vaccination up to 30 days post-last vaccination and from first vaccination up to study end will be summarized for all study groups. All AESIs will be summarized by MedDRA SOC and PT. A listing of AESIs will also be presented.

9.3.6.6. Suspected HZ episodes (for HZ/su and mRNA-1273 booster cohort only)

Number and percentage of participants reporting suspected HZ episodes from first dose to study end will be summarized for the HZ/suSeq and HZ/suCoAd study groups and overall. Potential HZ episodes throughout the entire study period will be listed by MedDRA PT.

9.3.6.7. COVID-19 cases

Number and percentage of participants meeting the case definitions of COVID-19 from first dose to study end will be summarized for all study groups (HZ/suSeq, HZ/suCoAd, FluD-QIVSeq, FluD-QIVCoAd and overall) and COVID-19 cases will also be listed.

9.3.6.8. Pregnancies

A listing of participants with confirmed pregnancies from first dose to study end will be provided for all study groups along with pregnancy details.

9.3.6.9. Withdrawals due to AEs and SAEs

Withdrawals due to solicited AEs, both local and systemic, unsolicited AEs, and SAEs will be presented in a listing.

9.3.7. Exploratory endpoints analyses

Anti-gE humoral immunogenicity at post-dose 1 of HZ/su:

Anti-gE antibody testing post-dose 1 may be limited, based upon the nature of the responses observed following the second dose of HZ/su and scientific relevance. Similar descriptive statistics will be presented for these results at 1 month post-dose 1 of HZ/su as described in Section 9.3.5.2.1.

Confirmed HZ cases (for HZ/su and mRNA-1273 booster cohort only):

- Number and percentage of participants reporting clinically confirmed HZ cases by PCR from first vaccination up to study end will be summarized for all study groups (HZ/suSeq, HZ/suCoAd, and overall).

Neutralizing antibodies (assuming if not assessed as a primary endpoint in all participants):

- GMT with 95% CI of SARS-CoV-2 neutralizing antibody concentrations in a sub-cohort of participants in each study group (HZ/suSeq, HZ/suCoAd, FluD-QIVSeq, FluD-QIVCoAd and overall) at pre-vaccination and 1 month post mRNA-1273 booster (at Week 4 for all groups). The sub-cohort (approximately 50 evaluable participants) will be selected post-hoc, based on other observed immune assay results.

Descriptive humoral immune responses to vaccination and/or SARS-CoV-2 infection:

- GMCs with 95% CI of anti-RBD protein antibodies at pre-vaccination and at 1 month post mRNA-1273 booster (at Week 4 for all study groups [HZ/suSeq, HZ/suCoAd, FluD-QIVSeq, FluD-QIVCoAd and overall]).

Descriptive humoral immune responses to SARS-CoV-2 infection:

- Anti-N seroconversion rate with exact 95% CI from pre-vaccination to 1 month post mRNA-1273 booster dose (at Week 4 for all study groups). Seroconversion is defined as a participant who is seronegative at baseline and seropositive post-vaccination OR for a participant seropositive at baseline, a 4-fold or more increase post-vaccination.

9.3.8. Other analyses

9.3.8.1. Demography and baseline characteristics analyses

For the HZ/su and mRNA-1273 booster study cohort, summaries of demographic characteristics will be produced for the HZ/su and mRNA-1273 Exposed Set and HZ/su and mRNA-1273 PPS by study group (HZ/suSeq and HZ/suCoAd and overall [i.e. both HZ/su groups]).

For the Flu D-QIV and mRNA-1273 booster study cohort, summaries of demographic characteristics will be produced for the Flu D-QIV and mRNA-1273 Exposed Set and Flu D-QIV and mRNA-1273 PPS by study group (FluD-QIVSeq, FluD-QIVCoAd and overall [i.e. both Flu D-QIV groups]).

Demographic characteristics (age at intervention in years, age category [50-59, 60-69, \geq 70 YOA for HZ/su and mRNA-1273 booster cohort; 18-64, \geq 65 YOA for Flu D-QIV and mRNA-1273 booster cohort] sex, and race and ethnicity) will be summarized by group using descriptive statistics:

- Frequency tables will be generated for categorical variables such as race.
- Mean, median, standard error, and range will be provided for continuous data such as age.

Withdrawal status will be summarized by study group using descriptive statistics for the HZ/su and mRNA-1273 Exposed Set and Flu D-QIV and mRNA-1273 Exposed Set only:

- The number of participants enrolled into the trial as well as the number of participants excluded from per-protocol analyses will be tabulated along with reasons for elimination. A listing of protocol deviations will be provided.
- CONSORT tables will be generated to show the dispositions of participants from the enrolled set to the exposed sets and from the exposed sets to the per protocol sets.
- The numbers of withdrawn participants will be tabulated according to the reason for withdrawal.

The percentage of participants using a concomitant medication/vaccination during the 7-day follow-up period and during the 30-day follow-up period after each intervention administration will be summarized.

9.4. Interim analyses

9.4.1. Sequence of analyses

The SRT will first review safety and reactogenicity data reported up to 7 days post-dose 1 of HZ/su when 10% of participants in the HZ/suCoAd group and 7 days post Flu D-QIV when 5% of participants in the FluD-QIVCoAd group have been vaccinated. Selected tabulations will be generated for SRT review to decide on continuation of enrollment in the co-administration groups. Limited safety analyses will be performed after all participants in the HZ/su and mRNA-1273 booster cohort sequential group have completed 14 days of follow-up after their HZ/su dose 1, and when all participants in the Flu D-QIV and mRNA-1273 cohort sequential group have completed 14 days of follow-up after their Flu D-QIV dose. Periodic analyses will be done for regular SRT review. All SRT analyses will be descriptive.

In addition to the SRT review, 1 formal interim analysis of safety, reactogenicity, and immunogenicity is planned.

9.4.2. First interim analysis

The first interim analysis will include analysis of safety, reactogenicity, and immunogenicity when the last participant enrolled in the HZ/su and mRNA-1273 booster cohort completes 6 weeks post-dose 2 of HZ/su Phone Contact 1. These participants will

also have completed the 4 weeks of follow-up post mRNA-1273 booster vaccine visit. Participants in the Flu D-QIV cohort will have also completed 4 weeks of follow-up post Flu D-QIV and post mRNA-1273 booster vaccine at this stage.

Analysis will be performed on data as clean as possible and clinical study report will be provided. Individual participant listings will be provided at this stage.

The first interim analysis will include:

- The assessment of non-inferiority of the humoral immune response to Dose 2 of HZ/su (HZ/suSeq and HZ/suCoAd groups).
- The assessment of non-inferiority of the humoral immune response to Flu D-QIV (FluD-QIVSeq and FluD-QIVCoAd groups).
- The assessment of non-inferiority of the humoral immune response to mRNA-1273 booster dose (both cohorts [HZ/su, Flu D-QIV], all groups [HZ/suSeq, HZ/suCoAd, FluD-QIVSeq, FluD-QIVCoAd]) (when co-administered with HZ/su and when co-administered with Flu D-QIV).
- Reactogenicity data after each administered vaccine dose (All groups: All doses of Flu D-QIV and mRNA-1273 booster dose; and all doses of HZ/su).
- Unsolicited AEs (serious and non-serious) safety data will also be included up to 30 days follow-up post each dose (All groups; including post all doses of Flu D-QIV and mRNA-1273 booster dose; and post all doses of HZ/su).
- SAEs, pIMDs, AESIs, suspected HZ episodes, IMCs, COVID-19 cases and pregnancies until the Data Lock Point (DLP) for all groups.

9.4.3. Final analysis

The **final analysis** will include safety follow-up up to 6 months post the last vaccine dose. At that time, an integrated study report will be written. Individual participant listings will be available at this stage.

9.4.4. Statistical considerations for interim analysis

Refer to Section 9.1 for details on type I error adjustments.

Hypothesis testing at the first interim analysis will occur in parallel within each cohort. The assessment of success for the confirmatory immunogenicity objective in the HZ/su and mRNA-1273 booster cohort will be made at the first interim analysis. Similarly, the determination of success for the confirmatory immunogenicity objective for the Flu D-QIV and mRNA-1273 booster cohort will be made at the first interim analysis.

9.5. Sample size determination

Assumptions used for the sample size calculations come from data available from prior studies ZOSTER-004 (117036), ZOSTER-042 (116887), ZOSTER-035 (116889), ZOSTER-048 (201198), ZOSTER-059 (204487), FLU D-QIV-008 (114269), FLU D-QIV-010 PRI (117276), and EXPLO-CRD-004, as well as preliminary mRNA-1273 Phase I and Phase II data [Jackson, 2020; Chu, 2021].

After final assay evaluations and validations, should the primary mRNA-1273 endpoint be replaced by SARS-CoV-2 neutralizing antibody titers, the same assumptions will be made since the standard deviation used for calculations was at the upper range of what has been observed for both endpoints; thus, the sample sizes presented below will remain for each cohort.

The type I error to be maintained is 0.025 (one-sided) for each study cohort (HZ/su and mRNA-1273 booster, Flu D-QIV and mRNA-1273 booster). Study success will be evaluated separately for each cohort. For the HZ/su and mRNA-1273 booster cohort, non-inferiority must be achieved for both hypothesis 1 and hypothesis 2. For the Flu D-QIV and mRNA-1273 booster cohort, success must be achieved for both hypothesis 3 and hypothesis 4.

A total of 1546 participants will need to be enrolled and randomized between the 2 cohorts.

9.5.1. Sample size for HZ/su and mRNA-1273 study cohort

The global power considers meeting the primary objectives in the HZ/su and mRNA-1273 booster cohort – with 245 evaluable participants in the HZ/suCoAd and HZ/suSeq groups the global power is approximately 90%. A GMC ratio of 1.1 between HZ/suSeq and HZ/suCoAd is assumed. Assuming 10% of the participants randomized are non-evaluable (e.g. due to drop out/protocol violation), approximately 546 participants will need to be randomized (273 participants each in the HZ/suCoAd and HZ/suSeq groups).

Note: If the dose of mRNA-1273 booster is adjusted while the study is ongoing, the sample size will be compensated in this cohort to ensure that there are enough evaluable participants in each group. (Amended 21 September 2021)

Sample size calculations for the HZ/su and mRNA-1273 booster study cohort can be found in [Table 18](#).

Table 18 Sample size calculations for HZ/su and mRNA-1273 booster study cohort

Endpoint	Number of Evaluable Participants per Cohort	α	Standard Deviation	Reference δ Assumed	NI δ	Total β	Power
Post dose 2 HZ/su Non-inferiority* (1-sided test) – Primary Endpoint							
Post-Dose 2 GMC Ratio (Sequential vs. Co-Ad) anti-gE	245	0.025	0.35	1.1	1.5	1.1%	98.9%
mRNA-1273 booster vaccine: Non-inferiority* (1-sided test) – Primary Endpoint							
GMC Ratio (Sequential vs. Co-Ad) anti-S	245	0.025	0.45	1.1	1.5	8.9%	91.1%
Global β to show non-inferiority of the primary endpoints						~10%	
Global power for the primary endpoints							~90%

Co-Ad = co-administered; GMC = geometric mean concentration

* Pass 2019: alpha = 2.5% for HZ/su and mRNA-1273 booster GMC ratio; Non-Inferiority -Two Independent Means – Two-sample T-tests for Non-Inferiority Assuming Equal Variance

For gE and mRNA-1273 booster vaccine: non-inferiority limit = 0.176 (=log10(1.5)), reference limit = 0.0413 (=log10(1.1)).

SDs for HZ/su Dose 2 are taken from the average of the reference co-administration studies ZOSTER-004 (117036), ZOSTER-042 (116887), ZOSTER-035 (116889), ZOSTER-048 (201198), ZOSTER-059 (204487), FLU D-QIV-008 (114269), FLU D-QIV-010 PRI (117276), and EXPLO-CRD-004. SDs for mRNA-1273 booster are taken from preliminary mRNA-1273 Phase I and II data.

9.5.2. Sample size for Flu D-QIV and mRNA-1273 booster study cohort

The non-inferiority of Flu D-QIV using GMTs (hypothesis 3) will be tested with a 1-sided type I error of 0.025 for all 4 strains in the Flu D-QIV vaccine. No adjustment is needed for the type I error due to multiple comparison of Flu D-QIV 4 strains since one wants to reject the null hypothesis if one comparison is not conclusive.

The non-inferiority of Flu D-QIV using SCR difference for 4 strains (Flu D-QIV and mRNA-1273 booster cohort secondary endpoint, hypothesis 5) will be tested using a sequential approach, meaning, hypothesis 3 and 4 (GMT, Flu D-QIV and mRNA-1273 booster primary endpoint) must be tested and non-inferiority of Flu D-QIV and mRNA-1273 booster using GMT ratio must be demonstrated before hypothesis 5 is tested. Both tests will use a type I error of 0.025. Study success on the Flu D-QIV and mRNA-1273 booster cohort will be declared if hypothesis 3 and 4 are met. Therefore, the power to achieve success for Flu D-QIV and mRNA-1273 booster cohort is driven by primary objectives for the Flu D-QIV and mRNA-1273 booster cohort.

A GMC ratio of 1.1 between FluD-QIVSeq and FluD-QIVCoAd is assumed for the mRNA endpoint. A GMT ratio of 1.04 between FluD-QIVSeq and FluD-QIV is assumed for the flu endpoint. The global power considers meeting both primary objectives in the Flu D-QIV and mRNA-1273 booster cohort –with 450 evaluable participants in the FluD-QIVCoAd and FluD-QIVSeq groups it is approximately 90.9%.

The nominal power for the secondary objective to demonstrate non-inferiority in terms of SCR difference for each strain in the Flu D-QIV vaccine between FluD-QIVSeq and FluD-QIVCoAd groups is at least 85%. Assuming 10% of the participants randomized are non-evaluable (e.g. due to drop out/protocol violation), approximately 1000 participants will need to be randomized (500 participants each in the FluD-QIVCoAd and FluD-QIVSeq groups).

Sample size calculations for the Flu D-QIV and mRNA-1273 booster study cohort can be found in [Table 19](#).

Table 19 Sample size calculations for Flu D-QIV and mRNA-1273 booster study cohort

Primary Endpoint	Number of Evaluable Participants per Group	α	Standard Deviation	Reference δ Assumed	NI δ	Total β	Power
FLU D-QIV Non-inferiority* (1-sided test) – 4 Strains – Primary Endpoint on GMT ratio							
GMT Ratio (Sequential vs. Co-Ad) – A/H1N1 strain	450	0.025	0.6	1.04	1.5	2.2%	97.8%
GMT Ratio (Sequential vs. Co-Ad) – A/H3N2 strain	450	0.025	0.6	1.04	1.5	2.2%	97.8%
GMT Ratio (Sequential vs. Co-Ad) – B/Victoria lineage	450	0.025	0.6	1.04	1.5	2.2%	97.8%
GMT Ratio (Sequential vs. Co-Ad) – B/Yamagata lineage	450	0.025	0.6	1.04	1.5	2.2%	97.8%
mRNA-1273 booster vaccine: Non-inferiority* (1-sided test) – Primary Endpoint							
GMC Ratio (Sequential vs. Co-Ad)	450	0.025	0.45	1.1	1.5	0.6%	99.4%
Global β to show non-inferiority of the primary endpoints						~9.1%	
Global power for the primary endpoints							~90.9%
FLU D-QIV Non-inferiority* (1-sided test) – 4 Strains – Secondary Endpoint on SCR difference							
Secondary Endpoint	Number of Evaluable Participants per Group	α	Threshold	SCR Assumed	Total β	Power	
SCR difference (Sequential vs. Co-Ad) – A/H1N1 strain	450	0.025	10%	78.6%	4.5%	95.5%	
SCR difference (Sequential vs. Co-Ad) – A H3N2 strain	450	0.025	10%	70.3%	9.2%	90.8%	
SCR difference (Sequential vs. Co-Ad) – B/Victoria lineage	450	0.025	10%	53.8%	14.9%	85.1%	
SCR difference (Sequential vs. Co-Ad) B/Yamagata lineage	450	0.025	10%	56.9%	14.0%	86.0%	

GMT = geometric mean titer; SCR = seroconversion rate

* Pass 2019: alpha = 2.5% for GMT/GMC ratio; Non-Inferiority -Two Independent Means – Two-sample T-tests for Non-Inferiority Assuming Equal Variance.

**Pass 2019: alpha = 2.5% for SCR difference; Non-inferiority: Proportions – Two independent Proportions – Non-Inferiority tests for Difference Between Two Proportions

For Flu D-QIV and mRNA-1273 booster vaccine: non-inferiority limit = 0.176 (=log10(1.5)), reference limit = 0.0413 (=log10(1.1)) for mRNA-1273 booster vaccine, reference limit = 0.017 (=log10(1.04)) for Flu D-QIV vaccine.

SCR Assumptions come from the US participants in the FLU D-QIV-008 study.

Participants who withdraw from the study will not be replaced.

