Hypothesis 4: The null hypothesis for this primary objective under consideration is UL of 95% CI for adjusted GMC ratio between FluD-QIVSeq and FluD-QIVCoAd group for anti-S protein antibody concentration at 1 month post mRNA-1273 booster dose (at Week 4 for FluD-QIVSeq and FluD-QIVCoAd) is ≥ 1.5 .

Success criteria - The objective will be met if the UL of the 95% CI of the adjusted GMC ratio between FluD-QIVSeq and FluD-QIVCoAd group for anti-S protein antibody concentration at 1 month post mRNA-1273 booster dose (at Week 4 for FluD-QIVSeq and FluD-QIVCoAd) is <1.5.

Secondary objective for Flu D-QIV and mRNA-1273 booster cohort:

The secondary objective for the Flu D-QIV and mRNA-1273 booster cohort will be assessed once the primary objective for Flu D-QIV and mRNA-1273 booster cohort is demonstrated. This will not be used to confirm study success, rather, for informative purposes to support the primary endpoint.

Hypothesis 5: The null hypothesis for this secondary objective under consideration is UL of the 95% CI of the SCR difference between FluD-QIVSeq and FluD-QIVCoAd group at 1 month post Flu D-QIV (at Week 6 for FluD-QIVSeq, at Week 4 for FluD-QIVCoAd) is $\geq 10\%$.

Success criteria: The objective will be met if the UL of the 95% CI of the SCR difference between FluD-QIVSeq and FluD-QIVCoAd group at 1 month post Flu D-QIV (at Week 6 for FluD-QIVSeq, at Week 4 for FluD-QIVCoAd) is <10% for each strain included in the Flu D-QIV vaccine.

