14.2.2. Flu Cohort

The primary power and sample size calculation assumes 10% of the participants randomized are non-evaluable (e.g. due to drop out/protocol violation). A range of non-evaluable rates were explored to demonstrate the power conferred by fewer evaluable participants in the study. The global power to meet both non-inferiority primary endpoints in the Flu D-QIV and mRNA-1273 booster cohort is maintained approximately 80% or above for non-evaluable rates of 25% or less.

The nominal power for the secondary objective to demonstrate non-inferiority in terms of SCR difference for each strain in the Flu D-QIV vaccine between FluD-QIVSeq and FluD-QIVCoAd groups is at least 75% across all of the non-evaluable rates explored (10%-30%).

Primary Endpoint Non-inferiority*	Non-evaluable Rate	Number of Evaluable Participants per Group	α (1-sided test)	Standard Deviation	Reference δ Assumed	NI δ	Total β	Power	Global β to show non- inferiority of the primary endpoints	Global power for the primary endpoints
FLU D-QIV GMT Ratio (Sequential vs. Co-Ad) – A/H1N1 strain	10%	450	0.025	0.6	1.04	1.5	2.2%	97.8%	~9.1%	~90.1%
FLU D-QIV GMT Ratio (Sequential vs. Co-Ad) – A/H3N2 strain	10%	450	0.025	0.6	1.04	1.5	2.2%	97.8%		
FLU D-QIV GMT Ratio (Sequential vs. Co-Ad) – B/Victoria lineage	10%	450	0.025	0.6	1.04	1.5	2.2%	97.8%		
FLU D-QIV GMT Ratio (Sequential vs. Co-Ad) – B/Yamagata lineage	10%	450	0.025	0.6	1.04	1.5	2.2%	97.8%		
mRNA-1273 booster GMC Ratio (Sequential vs. Co-Ad)	10%	450	0.025	0.45	1.1	1.5	0.6%	99.4%		
FLU D-QIV GMT Ratio (Sequential vs. Co-Ad) – A/H1N1 strain	15%	425	0.025	0.6	1.04	1.5	2.8%	97.2%	~11.5%	~88.5%
FLU D-QIV GMT Ratio (Sequential vs. Co-Ad) – A/H3N2 strain	15%	425	0.025	0.6	1.04	1.5	2.8%	97.2%		
FLU D-QIV GMT Ratio (Sequential vs. Co-Ad) – B/Victoria lineage	15%	425	0.025	0.6	1.04	1.5	2.8%	97.2%		
FLU D-QIV GMT Ratio (Sequential vs. Co-Ad) – B/Yamagata lineage	15%	425	0.025	0.6	1.04	1.5	2.8%	97.2%		
mRNA-1273 booster GMC Ratio (Sequential vs. Co-Ad)	15%	425	0.025	0.45	1.1	1.5	0.8%	99.2%		
FLU D-QIV GMT Ratio (Sequential vs. Co-Ad) – A/H1N1 strain	18%	410	0.025	0.6	1.04	1.5	3.3%	96.7%	~13.4%	~86.6%

FLU D-QIV GMT Ratio (Sequential vs. Co-Ad) – A/H3N2 strain	18%	410	0.025	0.6	1.04	1.5	3.3%	96.7%		
FLU D-QIV GMT Ratio (Sequential vs. Co-Ad) – B/Victoria lineage	18%	410	0.025	0.6	1.04	1.5	3.3%	96.7%		
FLU D-QIV GMT Ratio (Sequential vs. Co-Ad) – B/Yamagata lineage	18%	410	0.025	0.6	1.04	1.5	3.3%	96.7%		

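### SAP 14.2.2 misprints six power figures, and the 85% power quoted for the SCR objective is the lowest single-strain power, so it is a ceiling for Hypothesis 5

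*Protocol*

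**What the plan says.** - **Power statement.** Protocol 9.5.2: "The nominal power for the secondary objective to demonstrate non-inferiority in terms of SCR difference for each strain" is put at 85% or more. Table 19 gives the strain powers at 450 evaluable per group: A/H1N1 95.5%, A/H3N2 90.8%, B/Victoria 85.1%, B/Yamagata 86.0%. SAP 4.1.2 and its Table 4 repeat the statement and the figures.
- **Success criterion.** Protocol 9.1, Hypothesis 5: the upper limit of the 95% CI for the SCR difference "is <10% for each strain included in the Flu D-QIV vaccine".
- **Gate.** Protocol 9.5.2: non-inferiority under Hypotheses 3 and 4 "must be demonstrated before hypothesis 5 is tested".
- **Status.** Protocol 9.1 on this secondary objective: "This will not be used to confirm study success, rather, for informative purposes to support the primary endpoint".
- **Joint power.** Table 19 has a line headed "Global power for the primary endpoints", about 90.9%, covering the four GMT comparisons and the anti-S comparison. The SCR block has no such line.
- **Appendix.** SAP 14.2.2 repeats the tables at non-evaluable rates from 10% to 30% and gives the per-strain SCR power as at least 75% throughout.

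**The concern.** The criterion for Hypothesis 5 is joint, but the only power given for it is per strain. The chance that four tests all succeed cannot exceed the chance that the weakest one does. A figure offered as a minimum per strain is therefore a maximum for the objective. If Hypothesis 5 fails on one strain, a reader who expected at least 85% will take the failure as more informative than it is.

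The appendix figures are a simpler matter. Beta and power must add to 100%, and in six places in SAP 14.2.2 they do not. That appendix was added in SAP Amendment 1 to show power when more than 10% are non-evaluable, so its figures should be usable as printed.

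**Working it through.** **1. Reproduce the per-strain powers.** Inputs from Table 19: n = 450 per group, one-sided alpha 0.025, margin 10%, and the assumed SCR p. The true difference is not stated; the printed powers reproduce at zero. Power = Φ(0.10/√(2p(1−p)/n) − 1.96).

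| Strain | p | SE | Computed | Printed |
|---|---|---|---|---|
| A/H1N1 | 0.786 | 0.0273 | 95.5% | 95.5% |
| A/H3N2 | 0.703 | 0.0305 | 90.7% | 90.8% |
| B/Victoria | 0.538 | 0.0332 | 85.3% | 85.1% |
| B/Yamagata | 0.569 | 0.0330 | 85.7% | 86.0% |

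The printed strain powers hold.

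**2. Reproduce the plan's joint figure.** Four GMT tests at 97.8% and one anti-S test at 99.4%: 0.978⁴ × 0.994 = 0.909. This matches the printed 90.9%, so the plan's own global power for this cohort behaves as a product of single powers, although the documents do not state that rule.

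**3. All four SCR strains, before the gate, at 10% non-evaluable.**
- Independent strains: 0.955 × 0.908 × 0.851 × 0.860 = 0.635.
- Normal test statistics with the printed powers and an assumed common between-strain correlation of 0.3, 0.5, 0.7 or 0.9: 68.3%, 71.9%, 75.9% or 80.8%.
- Any dependence: from 1 − (0.045 + 0.092 + 0.149 + 0.140) = 57.4% up to the smallest single power, 85.1%.

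**4. Including the gate**, at the plan's assumed GMT ratio of 1.04 and anti-S GMC ratio of 1.1.
- All nine tests independent: 0.635 × 0.909 = 0.577.
- Assumed between-strain correlation / GMT-SCR correlation within strain of 0.3/0.5, 0.5/0.7 or 0.9/0.7, with anti-S independent: about 65%, 70% or 79%.
- Any dependence: from 0.574 − 4 × 0.022 − 0.006 = 48.0% up to 85.1%.

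**5. At 30% non-evaluable, before the gate.** Independent strains: 0.896 × 0.827 × 0.764 × 0.766 = 0.434. The ceiling is 76.4%.

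**6. SAP 14.2.2, pairs that do not add to 100%.** The formula in step 1, applied at each row's n, shows which SCR column is wrong.

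| Row | Printed beta | Printed power | Sum | Recomputed power | Correct beta |
|---|---|---|---|---|---|
| 20%, B/Victoria (n = 400) | 19.8 | 81.2 | 101.0 | 81.0 | 18.8 |
| 20%, B/Yamagata (n = 400) | 19.6 | 81.4 | 101.0 | 81.5 | 18.6 |
| 25%, B/Victoria (n = 375) | 12.0 | 78.0 | 90.0 | 78.4 | 22.0 |
| 25%, B/Yamagata (n = 375) | 10.7 | 79.3 | 90.0 | 79.0 | 20.7 |
| 30%, A/H3N2 (n = 350) | 11.3 | 82.7 | 94.0 | 82.5 | 17.3 |

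The printed powers reproduce to within 0.4 points, so the betas are the errors. The sixth figure is in the 10% primary block: global beta 9.1% stands beside global power 90.1% (sum 99.2%). Step 2, Protocol Table 19 and SAP Table 4 all give 90.9%, so here the power is the misprint.

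**The case against.** The power statement carries both qualifiers, nominal and per strain, and the table below it lists all four values. A reader might infer that 85% was miscalculated. It was not: it reproduces, and it is what its label says.

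The plan also has a reason for giving joint power only for the primary endpoints. Hypothesis 5 does not confirm study success, and Protocol 9.5.2 says that power for success in this cohort is driven by the primary objectives. A reader might conclude that the cohort is underpowered or too small. The documents do not support that, because the sample size rests on Hypotheses 3 and 4, whose 90.9% reproduces. Nor can the wording affect the design now: SAP section 11 reports the safety interim as already done.

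Finally, a reader might take 58% as the power of Hypothesis 5. That figure requires GMT and SCR results for a strain to be independent, yet both derive from the same HI titres in the same participants. Plausible correlation raises it to about 65% to 79%. The documents give no correlations, so 58% is one scenario, not an estimate.

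What survives is narrower. The labels do not supply the power of the criterion actually applied, and no degree of correlation takes that power above 85.1%. The six misprints need no assumption at all.

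**Conclusion.** The point holds, at minor severity. Six printed figures in SAP 14.2.2 are wrong: the five betas by 1, 1, 10, 10 and 6 points, and the global power by 0.8 points. None alters a printed per-strain power or the 75% per-strain statement.

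The 85% in Protocol 9.5.2 and SAP 4.1.2 is right as a per-strain minimum and incomplete as a power for Hypothesis 5, for which it is an upper bound. The same applies to the 75% in SAP 14.2.2.

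The ceiling rests only on the printed powers. The other joint figures rest on a true SCR difference of zero in every strain and on assumed correlations, and those that include the gate also use the plan's GMT and GMC ratios. Combining a GMT ratio of 1.04 with no SCR difference follows the plan's inputs, but they are not a single coherent scenario.

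**What to change.** 1. SAP 14.2.2, betas: 20% B/Victoria to 18.8%, 20% B/Yamagata to 18.6%, 25% B/Victoria to 22.0%, 25% B/Yamagata to 20.7%, 30% A/H3N2 to 17.3%. Global power in the 10% row: to about 90.9%.
2. Protocol 9.5.2 and SAP 4.1.2, replace the power statement with:

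> The lowest nominal per-strain power is 85% (B/Victoria). With a true SCR difference of zero in every strain, the power for all four strains to meet the criterion, before the gate on Hypotheses 3 and 4, is about 63% if strains are independent, about 68% to 81% for assumed common between-strain correlations of 0.3 to 0.9, and never above 85.1%. Including the gate (assumed GMT ratio 1.04, anti-S GMC ratio 1.1) it is lower: about 58% if all tests are independent, and about 65% to 79% for assumed between-strain correlations of 0.3 to 0.9 with a within-strain GMT-SCR correlation of 0.5 to 0.7.

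3. SAP 14.2.2: label the 75% as the lowest per-strain power, and add that the all-four-strain power is lower (at 30% non-evaluable, about 43% before the gate if strains are independent, and at most 76.4%).

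A full table of gated powers under independence is not worth adding, since that assumption is the least credible one. The cost is six number corrections and a few sentences. Sample size, success criterion and analysis do not change.
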